Statistical Methods	
Analysis Populations The transplanted recipient population will consist of all recipients who are transplanted. The Per-Protocol (PP) population will consist of all recipients who are transplanted without a major protocol violation. The primary analyses of all effectiveness and safety endpoints will be based on the Per Protocol population. Supportive analyses for all endpoints will be provided for the transplanted recipient population
 
Effectiveness There are two co-primary hypotheses for this trial.
 
 • Co-Primary Hypothesis #1 The first co-primary hypothesis is that the proportion of transplanted recipients of lungs preserved using the OCSTM Lung System surviving at Day 30 and at initial hospital discharge post-transplantation (whichever occurs later) is greater than a performance goal based on the corresponding proportion of patients in the Per-Protocol population of the Control arm of the INSPIRE trial (0.939) with a margin of 0.12 (12%). The formal statistical hypothesis test is as follows: $H_0: \pi_{OCS\ Lung} \leq 0.819$ $H_1: \pi_{OCS\ Lung} > 0.819$ where $\pi_{OCS\ Lung}$ is the proportion of transplanted recipients alive Day 30 and at initial hospital discharge. This co-primary effectiveness endpoint will be summarized using a count and percentage with an exact 95% confidence interval for the percentage based on the binomial distribution. A one-sided exact binomial test at the 0.025 significance level will be performed to test the null hypothesis H_0. • Co-Primary Hypothesis #2 The second co-primary hypothesis is that the Utilization Rate (defined above) is greater than a performance goal of 0.54 (54%), which is based on the utilization rate reported for XVIVO in the NOVEL Trial (FDA Executive Summary for XVIVO, p.53). The formal statistical hypothesis test is as follows: $H_0: \pi_{OCS\ Lung} \leq 0.54$ $H_1: \pi_{OCS\ Lung} > 0.54$ where $\pi_{OCS\ Lung}$ is the observed utilization rate in the EXPAND trial. This co-primary effectiveness endpoint will be summarized using a count and percentage with an exact 95% confidence interval for the true percentage based on the binomial distribution. A one-sided exact binomial test at the 0.025 significance level will be performed to test the null hypothesis, H_0. 
Secondary Effectiveness Endpoints The secondary effectiveness endpoints will be summarized using counts and percentages and an exact 95% confidence interval for the true percentage based on the binomial distribution.
 
Safety Safety will be analyzed principally by examination of the frequency of adverse events. In particular, the number of lung graft-related serious adverse events (SAEs) up to the 30-day follow-up or until initial hospital admission (if longer than 30 days) after transplantation per subject will be analyzed. This endpoint is defined to consist of the following adverse events (at most one per type), if they are serious adverse events (as defined in Appendix 3):
 
 • Acute rejection

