1.4.4. OCSTTM Lung System Testing - EXPAND

The Lung EXPAND I study is a single arm, international study of 79 lung transplant recipients enrolled at 8 sites as of December 7, 2016. This investigational study evaluated the safety and effectiveness of the TransMedics OCSTTM Lung System to recruit, preserve, assess, and transport non-ideal donor lungs that do not meet the current standard donor lung acceptance criteria for transplantation into a recipient.

The study is on-going and preliminary results have been presented at the 2016 ISHLT meeting (Loor, et al.).⁵⁴ The most recent accepted FDA progress report provides the data on all patients transplanted through April 19, 2016 and followed through 30 days post-transplantation. Sixty-two (62) subjects had been transplanted (42 in the U.S.). For fifty-six (56) patients the 30-day post-transplant timepoint has been reached (one patient expired) while six are still within the 30-day window. Seventy-two (72) donor lungs have been retrieved with 62 transplanted and 10 not transplanted. Of the 10 preserved lungs not transplanted, 5 were from DCD donors, 5 from donors with age > 55, 2 with low P/F ratio, and 2 from donors with >6 hours cross clamp time.

Two (2) of the 10 donor lungs were not transplanted due to reasons unrelated to lung condition. In both cases, the lungs performed well on OCSTM and would have been suitable for transplant, but were not used due to issues with the recipient. Therefore, the utilization rate for these non-ideal donor organs is 88.6% (62/70).

Donor lung characteristics are shown Table 2 below. The retrieved donor lungs met several eligibility criteria including donor age > 55 years (43%), expected cross clamp time > 6 hours for the second lung (38%), PaO₂/FiO₂ < 300 mm Hg at final offer (29%) and Donation after Circulatory Death (DCD) (30%).

Table 2: Donor Lung Characteristics in EXPAND I

	OCS Lung Transplants (n=56)
Age (Years): Mean \pm SD	48.0 \pm 15.7
Donor Eligibility Criteria	
PaO ₂ /FiO ₂ Ratio \leq 300 mmHg	29%
Expected Cross Clamp Time > 6 hours	38%
DCD Donor	30%
Donor Age >55 yr	43%
> 1 Eligibility Criteria (from above list)	34%

There is 98% survival of subjects at 30 days and 95% survival of subjects during the initial hospitalization.

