9.2.2. Per-Protocol (PP) Population

The Per-Protocol (PP) population will consist of all subjects who are transplanted without a major protocol violation. Major protocol violations would be considered:

- Ineligible for the study according to the recipient inclusion and exclusion criteria
- Ineligible for the study according to the donor organ inclusion and exclusion criteria
- Failure to complete adequate post-transplant assessments to support the primary effectiveness and primary safety endpoints
- Failure to follow the IFU for the OCSTM Lung System
- Failure to meet Donor Lung Acceptance for Transplantation after assessment on the OCSTM Lung System, as outlined in Section 6.5.

The primary analysis of all endpoints will be based on the PP population, which is appropriate given that the comparator rate is derived from the Control arm of the PP population from the INSPIRE trial. Supportive analyses will be conducted using the Transplanted Recipient population.

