9.3.2. Co-primary Effectiveness Endpoint #2

The second co-primary hypothesis is that the Utilization Rate (defined in Section 4.1 above) is greater than a performance goal of 0.54 (54%), which is based on the utilization rate reported for XVIVO in the NOVEL Trial.² The formal statistical hypothesis test is as follows:

$$H_0: \pi_{OCS\ Lung} \leq 0.54$$

$$H_1: \pi_{OCS\ Lung} > 0.54$$

where $\pi_{OCS\ Lung}$ is the observed utilization rate in the EXPAND trial.

The appropriateness of the performance goal of 54% is based on the following:

- The 54% rate is the only published data available on utilization rate for non-ideal donor lungs.⁵⁶
- The donor lung inclusion/exclusion criteria are similar to those used for the XVIVO NOVEL study. Where differences exist, they tend to make the donor lungs more challenging for EXPAND II vs NOVEL. For example:
 - EXPAND II will enroll DCD donors with any $\text{PaO}_2/\text{FiO}_2$ ratio, while the NOVEL study only included DCD donors with $\text{PaO}_2/\text{FiO}_2$ ratio ≥ 300 mmHg.
 - EXPAND II will include older donors (age > 55 years) while NOVEL did not have an inclusion criterion based on donor age. Donor age > 55 years old is known to have a negative impact on outcomes after lung transplantation.⁴
- Finally, this co-primary endpoint is designed to show superiority of the OCSTM Lung System to the XVIVO EVLP device. Demonstrating superiority to the only published data on utilization in the non-ideal donor lung population is a rigorous and appropriate test of a new technology.

This co-primary effectiveness endpoint will be summarized using a count and percentage with an exact 95% confidence interval for the true percentage based on the binomial distribution. A one-sided exact binomial test at the 0.025 significance level will be performed to test the null hypothesis, H_0 .

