## 4. EFFECTIVENESS AND SAFETY ENDPOINTS

### 4.1. Primary Effectiveness Endpoint

The study will evaluate two co-primary effectiveness endpoints:

- Patient survival at both 30 days and at initial hospital discharge post-transplantation, whichever occurs later. The basis for this endpoint is the control arm of the INSPIRE trial with a 12% margin.
- Utilization Rate, defined as the number of donated lungs instrumented on OCS™ that meet inclusion/exclusion criteria for the trial and acceptance criteria for transplantation after OCS™ Lung assessment divided by the total eligible donor lungs instrumented on the OCS™ Lung System. The basis for this endpoint is the utilization rate reported for XVIVO in the NOVEL Trial.

Survival at initial hospital discharge post-transplantation is considered to be survival during the initial hospital admission for the transplant procedure through the date of discharge, if it is longer than 30 days.

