### **6. ANALYSIS POPULATIONS**

#### **6.1. Transplanted Recipient Population**

The transplanted recipient population will consist of all subjects who are transplanted in the trial. Additional supportive analyses of all effectiveness and safety endpoints will be based on the transplanted recipient population.

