#### **6.2. Per-Protocol (PP) Population**

The Per-Protocol (PP) population will consist of all subjects who are transplanted without a major protocol violation. Major protocol violations would be considered:

- Ineligible for the study according to the recipient inclusion and exclusion criteria
- Ineligible for the study according to the donor organ inclusion and exclusion criteria
- Failure to complete adequate post-transplant assessments to support the primary effectiveness and primary safety endpoints
- Failure to follow the IFU for the OCS™ Lung System
- Failure to meet Donor Lung Acceptance for Transplantation after assessment on the OCS™ Lung System, as outlined in Section 6.5 of the Protocol.

The primary analysis of all effectiveness endpoints will be based on the PP population, which is appropriate given that the comparator rate is derived from the Control arm of the PP population from the INSPIRE trial. Supportive analyses will be conducted using the Transplanted Recipient population.

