## 12.2. Co-Primary Effectiveness Endpoint #2

The second co-primary hypothesis is that the Utilization Rate (defined in Section 4.1 above) is greater than a performance goal of 0.54 (54%), which is based on the utilization rate reported for XVIVO in the NOVEL Trial. The formal statistical hypothesis test is as follows:

$$H_{02}: \pi_{OCS\ Lung} \leq 0.54$$

$$H_{12}: \pi_{OCS\ Lung} > 0.54$$

where  $\pi_{OCS\ Lung}$  is the observed utilization rate in the EXPAND trial.

The appropriateness of the performance goal of 54% is based on the following:

- The 54% rate is the only published data available on utilization rate for non-ideal donor lungs.
- The donor lung inclusion/exclusion criteria are similar to those used for the XVIVO NOVEL study. Where differences exist, they tend to make the donor lungs more challenging for EXPAND II vs NOVEL. For example:
  - EXPAND II will enroll DCD donors with any  $\text{PaO}_2/\text{FiO}_2$  ratio, while the NOVEL study only included DCD donors with  $\text{PaO}_2/\text{FiO}_2$  ratio  $\geq 300$  mmHg.
  - EXPAND II will include older donors (age  $> 55$  years) while NOVEL did not have an inclusion criterion based on donor age. Donor age  $> 55$  years old is known to have a negative impact on outcomes after lung transplantation.
- Finally, this co-primary endpoint is designed to show superiority of the OCS™ Lung System to the XVIVO EVLP device. Demonstrating superiority to the only published data on utilization in the non-ideal donor lung population is a rigorous and appropriate test of a new technology.

This co-primary effectiveness endpoints will be summarized for the PP and Transplanted Recipient Populations using a count and percentage with an exact (Clopper-Pearson) 95% confidence interval for the true percentage based on the binomial distribution. A one-sided exact binomial test at the 0.025 significance level will be performed to test the null hypothesis,  $H_{02}$ .

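### Co-primary endpoint #2 is defined over all eligible instrumented donor lungs but assigned to populations that hold only transplanted recipients, so its primary per-protocol test cannot fail

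*SAP*

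**What the plan says.** **Definition.** SAP 4.1 and Protocol 4.1 take, as numerator, the instrumented lungs that satisfy trial eligibility and the post-OCS acceptance criteria, "divided by the total eligible donor lungs instrumented on the" OCS. A lung that is perfused, assessed and turned down stays in the denominator. SAP 12.2 and Protocol 9.3.2 both carry this definition into the hypothesis by cross-reference: "that the Utilization Rate (defined in Section 4.1 above) is greater than" 54%.

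**Analysis set.** The closing paragraph of SAP 12.2 reads: "This co-primary effectiveness endpoints will be summarized for the PP and Transplanted Recipient Populations using a count and percentage". SAP 6.1 says: "The transplanted recipient population will consist of all subjects who are transplanted in the trial". SAP 6.2 limits PP to transplanted subjects without a major violation, and the listed violations include donor ineligibility and failure of the Protocol 6.5 acceptance criteria. SAP 6.2 then adds: "The primary analysis of all effectiveness endpoints will be based on the PP population". Protocol 9.2.2 is broader, "The primary analysis of all endpoints will be based on the PP population", and the synopsis agrees: "The primary analyses of all effectiveness and safety endpoints will be based on the Per Protocol population". None of these statements excepts utilization.

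**What is absent.** Neither document defines a donor-lung analysis population. SAP 7 summarises disposition for eligible donors, but only descriptively. Protocol 9.3.2 names no population for this endpoint.

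**Sample size.** SAP 3.4 and Protocol 9.7 size this endpoint at 84, expressed as transplanted recipients, for 0.54 versus 0.72 with a one-sided exact binomial test at 0.025 and 90% power.

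**The concern.** The definition and the analysis set cannot both be followed. Turned-down lungs have no transplanted recipient, so they cannot enter either named population. Under Protocol 6.3 a subject number is assigned only after the lungs have met the criteria on the OCS. PP also removes recipients of ineligible lungs or of lungs that failed acceptance, so every lung left in PP is a numerator lung and the rate is 100% by construction. In the Transplanted Recipient set the rate can fall below 100% only through lungs transplanted despite failing those criteria.

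This is the primary test of a co-primary hypothesis. On the literal PP reading, the null of utilization at or below 54% is rejected whatever the true utilization. On the SAP 4.1 reading the test is informative and can fail. The effect may reach the overall conclusion: SAP 3.4 and Protocol 9.7 also call the study successful when only the smaller of the two p-values clears 0.0125, and a guaranteed tiny p-value for utilization would meet that rule even if survival missed its goal.

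Two smaller points follow from the same confusion of units. The 84 for utilization is a number of lungs but is labelled as recipients. The handling of lungs that meet acceptance but go unused should also be stated, because EXPAND I (Protocol 1.4.4) left two such lungs out of both counts.

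**Working it through.** **Inputs.** p0 = 0.54, p1 = 0.72, one-sided alpha 0.025, exact binomial, N = 84, planned enrolment 90 transplants (SAP 3.4, SAP 12.2). EXPAND I: 72 lungs retrieved, 62 transplanted, 2 unused for reasons unrelated to the lung (Protocol 1.4.4).

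**1. Reproducing the plan's 84.** The critical value r is the smallest r with P(X ≥ r | n, 0.54) ≤ 0.025; power is P(X ≥ r | n, 0.72).
- n = 84: r = 55, exact size 0.0219, power 0.925.
- n = 83: r = 55, power 0.899.
- Exact power is not monotone in n. It first touches 90% at n = 76 (0.907), and n = 84 is the smallest n from which it stays at or above 90% (checked to 134).

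The 84 is therefore right as the denominator of the Utilization Rate, that is, as instrumented lungs.

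**2. Literal PP reading.** All n lungs are successes, so p = 0.54^n and the Clopper-Pearson lower bound is 0.025^(1/n).
- n = 84: p = 0.54^84 = 3.3e-23; lower bound 0.025^(1/84) = 0.957.
- n = 90: p = 0.54^90 = 8.2e-25; lower bound 0.960.

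The number of turned-down lungs does not enter either formula.

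**3. Literal Transplanted Recipient reading, n = 90.** 59/90 gives p = 0.017 and 58/90 gives p = 0.029. The test fails only if at least 90 − 58 = 32 lungs were transplanted despite failing acceptance.

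**4. SAP 4.1 reading, 90 accepted lungs out of N instrumented.** p = P(X ≥ 90 | N, 0.54).

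| N instrumented | Rate | p, SAP 4.1 reading | Result | Shown in a PP set of 90 as |
|---|---|---|---|---|
| 125 | 72.0% | 2.8e-5 | pass | 90/90 |
| 144 | 62.5% | 0.024 | pass | 90/90 |
| 145 | 62.1% | 0.030 | fail | 90/90 |
| 150 | 60.0% | 0.081 | fail | 90/90 |
| 225 | 40.0% | >0.999 | fail | 90/90 |

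N = 125 follows from 90/0.72. The other values are illustrative or mark the boundary, and the last column assumes all 90 accepted lungs are transplanted into PP recipients.

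**5. Power once the denominator is lungs.**
- If every accepted lung is transplanted, 90 transplants at 72% imply 90/0.72 = 125 instrumented lungs: r = 79, size 0.0236, power 0.987.
- If 2 of every 64 suitable lungs go unused, as in EXPAND I, 90/(62/64) = 92.9, so about 93 accepted and 92.9/0.72 = 129 instrumented: r = 82, power 0.986.
- If enrolment simply stops at 90 accepted lungs, the chance of needing no more than 144 instrumented lungs at a true 72% is 0.995.

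The unit slip costs no power.

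**6. Accepted but unused lungs.** EXPAND I reported 62/70 = 88.6%. SAP 4.1 read literally would give 64/72 = 88.9% if both unused lungs met acceptance.

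**The case against.** The strongest reply is that the intent is plain. The definition is the same in the synopsis, Protocol 4.1 and SAP 4.1. The hypothesis cites it directly. Protocol 9.3.2 names no recipient population, and SAP 3.5 declares no change from the protocol. A 72% planning rate makes no sense for an n/n quantity. The reason given for PP primacy, a comparator from the INSPIRE PP control arm, does not fit an endpoint benchmarked to NOVEL. On this view SAP 12.2 merely repeats the population sentence from SAP 12.1, and no one would report n/n as a utilization rate. All of this stands as evidence of intent. It does not remove the conflict: the SAP's only population instruction for this test points to recipients, and SAP 6.2 reinforces it without exception.

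A second reply offers a reading said to keep both instructions: lungs of PP recipients over all eligible instrumented lungs. That test could fail. But its numerator is lungs transplanted into PP recipients, whereas SAP 4.1 counts lungs that meet acceptance. It therefore departs from the definition and shows that a third analysis is also open.

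Three narrower objections are fair. The sample-size label has no numerical consequence. SAP 4.1 already settles accepted but unused lungs, so that needs only confirmation. Finally, Protocol 6.3 calls lungs ineligible when the retrieval team finds them unsuitable, without saying that this applies only before instrumentation; applied afterwards, it could remove turned-down lungs from the denominator again. The fix should close that gap.

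**Conclusion.** The concern holds and should be corrected before the data are analysed. As written, the primary PP analysis of co-primary endpoint #2 is 100% by construction and rejects its null with certainty (84/84, p = 3.3e-23). The analysis evidently intended can fail: with 90 accepted lungs it does so from 145 instrumented lungs upward. The PP result rests on reading SAP 6.2 and 12.2 literally; the pass/fail boundary rests on 90 accepted lungs and the SAP 4.1 denominator. The intended denominator can be recovered from the rest of the plan, so correction is easy, but the choice should not be left to whoever programs the analysis once results are known. The sample size is adequate: 84 is correct as a count of lungs, and 90 transplants at the assumed 72% give power of about 98.6% to 98.7%. The 84 label is an error of wording only, and the accepted-but-unused question is minor (88.6% against 88.9% in EXPAND I).

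**What to change.** 1. In SAP 6 and Protocol 9.2, add a Donor Lung Population: all eligible donor lungs (pairs) instrumented on the OCS, whether or not transplanted.
2. State that eligibility for this set is fixed before instrumentation, so that a lung turned down after OCS assessment stays in the denominator.
3. In SAP 12.2, replace the two recipient populations with the Donor Lung Population, and name it as the primary set for co-primary endpoint #2 in Protocol 9.3.2 and the synopsis.
4. Except the Utilization Rate from the PP-primary statements in SAP 6.2, Protocol 9.2.2 and the synopsis.
5. Confirm that lungs meeting acceptance but not transplanted for logistical or recipient reasons (Protocol 6.3) count in both numerator and denominator, as SAP 4.1 reads.
6. In SAP 3.4, Protocol 9.7 and the synopsis, restate the requirement for this endpoint as 84 instrumented donor lungs.

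**Cost.** Wording changes in the SAP, protocol and synopsis. The protocol part is an amendment and goes through ethics review under Protocol 17. No patients or data are added: Protocol 6.2 already records donor data for instrumented lungs, Appendix 4 already collects reasons for non-transplant, and SAP 7 already summarises disposition for eligible donors.

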### **12.3. Secondary Effectiveness Endpoints**

The study will evaluate the following secondary effectiveness endpoints:

- Incidence of Primary Graft Dysfunction (PGD) Grade 3 at T72 hours
- Incidence of PGD Grade 3 within the initial 72 hours post-transplantation
- Incidence of Primary Graft Dysfunction (PGD) Grades 2 or 3 at T72 hours
- Incidence of PGD Grades 2 or 3 within the initial 72 hours post-transplantation.

The secondary effectiveness endpoints will be summarized for the PP and Transplanted Recipient Populations using counts and percentages and an exact (Clopper-Pearson) 95% confidence interval for the true percentage based on the binomial distribution.

### **12.4. Other Effectiveness Endpoints**

Other effectiveness endpoints are as follows:

- Total ischemia and cross-clamp times
- Duration of initial post-transplant invasive mechanical ventilation
- Length of initial post-transplant ICU stay
- Length of initial post-transplant hospital stay
- PGD Scores at T0, T24, T48, and T72 hours
- Incidence of BOS at 6, 12, 24, and 36 months post-transplantation (including post-market follow-up)
- All-cause mortality at 6, 12, 24, and 36 months post-transplantation (including post-market follow-up)
- Lung graft-related mortality at 6, 12, 24, and 36 months post-transplantation (including post-market follow-up).

These endpoints will be summarized for the PP and Transplanted Recipient Populations using descriptive statistics and 95% confidence intervals for the true mean based on the t-distribution for continuous endpoints and using counts and percentages and exact (Clopper-Pearson) 95% confidence intervals for categorical endpoints.

Survival will also be displayed using the Kaplan-Meier product-limit method.

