7.3. Long-Term Follow-up: 6, 12, 24, and 36 months (Post-Market Follow-up)

Follow-up data collection will be conducted at approximately 6, 12, 24, and 36 months post-transplant.

- **6, 12, 24, and 36 month Follow Up:** At approximately 6, 12, 24, and 36 months post-transplant, the patient will be evaluated at an office visit if this is the institution's standard of care, and, if not, by phone contact by the site. The patient's medical record will be reviewed to confirm patient's answers. This follow-up will collect the following information on transplanted recipients in the trial:
 - Patient and graft survival
 - Whether the patient was hospitalized after initial discharge, and, if so, the primary reason for the hospitalization and the length of stay; these data will be collected only for the 6-month follow-up timepoint.
 - Clinical diagnosis of BOS and method of diagnosis
 - Results of any standard of care or per-cause pulmonary function tests, bronchoscopies, or biopsies

The 6, 12, 24, and 36 months follow-up will be collected within +30 days of the designated period and will be recorded.

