## 3. STUDY DESIGN

### 3.1. Overview

This is a prospective, pivotal, international, single-arm trial of donor lungs and donor lung transplant recipients.

The proposed clinical trial seeks to evaluate the safety and effectiveness of the OCS™ Lung System for donor lungs that today may not be transplanted due to the limitations associated with cold storage technique (such as ischemia and the inability to evaluate organ function following cold preservation). The results of the OCS™ Lung System with non-ideal donor lungs in this study will be compared to the results for both the control arm of the INSPIRE trial and to the results of the NOVEL study of the XEVIVO EVLP system.

Subjects will be followed for up to 36 months from the date of transplantation. The details of the follow-up are summarized in Appendix 4 of the Protocol as follows:

- All subjects will be followed from transplant to discharge.
- Patient survival will be documented on Day 30 post-transplant and at initial hospital discharge following transplantation (if longer than 30 days).
- Patient survival and clinical diagnosis of BOS will be documented at 6, 12, 24, and 36 months patient follow-up (these are post-market follow-up timepoints) per Appendix 4 of the Protocol.

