### **3.4. Determination of Sample Size**

The sample size for this trial was determined based on providing adequate statistical power for hypothesis testing of the two co-primary effectiveness endpoints. All sample size calculations were performed using PROC POWER in SAS.

For the first co-primary endpoint, the calculations assumed a one-sided exact binomial test, an alpha level of 0.025, a control-based rate of 0.939 with a margin of 0.12 (to derive the performance goal of 0.819), a true survival rate for OCS™ of 0.939, and desired power of 90%. Based on these specifications, the required sample size was determined to be 84 transplanted recipients.

For the second co-primary endpoint, the calculations assumed a one-sided exact binomial test, an alpha level of 0.025, a performance goal of 0.54, a utilization rate of 72% for OCS™, and desired 90% power. Based on these specifications, the required sample size was determined to be 84 transplanted recipients

In order to ensure that a sufficient number of subjects are evaluable in the per-protocol population of the trial, 90 transplanted recipients in the study are expected to provide adequate power to evaluate the two co-primary effectiveness objectives given the assumptions described.

Due to multiple primary endpoints, the Hochberg Method will be used to control familywise error. The p-values for each of the co-primary endpoints will be ordered from highest to lowest. If the highest p-value is less than 0.025 then both endpoints achieve statistical significance and the null hypothesis of each co-primary endpoint can be rejected. If not, then the lower of the two p-values will be assessed against a significance level of 0.0125. If the adjusted significance level of 0.0125 is applied to any of the co-primary endpoints, the power of that analysis will be greater than 85%. Therefore, the study will be considered successful in either of the two scenarios described above.

With regard to the primary safety endpoint, the pre-specified safety margin of 0.7 events per patient, the estimated mean of 0.29 events per patient (with an estimated standard deviation of 2.0), a one-sided alpha of 0.025, and the sample size of 90 transplanted recipients results in power greater than 90% when considering a one-sample t-test on the mean.

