#### **5.3. Handling of Dropouts and Missing Data**

Missing outcomes, although not expected, will be addressed through multiple imputation so that analyses are based on complete data. The following covariates will be used to impute missing outcomes:

- Donor PaO2/FiO2 ratio at the time of the offer: ( $\leq 300$ ,  $> 300$ )
- Expected cross-clamp time for the second lung: ( $\leq 6$  hours,  $> 6$  hours)
- Donor after cardiac death (DCD donor): (Yes, No)
- Donor Age: ( $< 55$  years,  $\geq 55$  years)
- Recipient Gender: (Male, Female)

- Recipient Age

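### Mortality at 6 to 36 months is tabled as simple percentages, with missing outcomes imputed from baseline covariates only; if dropout is unrelated to death risk this overstates the later rates

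*SAP*

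**What the plan says.** SAP 12.4 lists all-cause mortality and lung graft-related mortality, each at 6, 12, 24 and 36 months, among the other effectiveness endpoints. Both are yes/no outcomes at each time point, so they are summarised "using counts and percentages and exact (Clopper-Pearson) 95% confidence intervals for categorical endpoints", for the Per-Protocol and Transplanted Recipient populations. The section then adds: "Survival will also be displayed using the Kaplan-Meier product-limit method".

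For incomplete data, SAP 5.3 states: "Missing outcomes, although not expected, will be addressed through multiple imputation so that analyses are based on complete data". It continues "The following covariates will be used to impute missing outcomes" and names six: the four donor criteria (PaO2/FiO2, expected cross-clamp time, DCD status, donor age), recipient gender and recipient age. All are fixed at baseline. Follow-up time and last known vital status are not listed, and the rule is not restricted to short-term endpoints.

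On follow-up, SAP 3.1 states: "Subjects will be followed for up to 36 months from the date of transplantation". Protocol 7.3 sets the contact times: "The 6, 12, 24, and 36 months follow-up will be collected within +30 days of the designated period".

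SAP 14 gives Kaplan-Meier probabilities at Day 30 and at 6, 12, 24 and 36 months for freedom from BOS and for BOS-free survival. It names none for overall survival.

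**The concern.** A recipient who leaves the study alive after month 24 has a missing 36-month outcome. An imputation model that sees only baseline covariates gives that person the death risk of the whole 36 months, although most of that time has already been survived.

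The risk it assigns is itself too high. Among recipients with known status at month 36, every death before dropout is counted, but a survivor counts only if followed all the way. Both effects push the completed percentage upward when dropout has nothing to do with prognosis.

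The report could then carry two mortality figures that disagree, a tabled percentage and a Kaplan-Meier curve, and the SAP does not say which is the reported mortality. It also does not say whether a recipient censored before month 36 counts as a missing outcome. The trial has a single arm, so no concurrent control group carries the same bias. Lung graft-related mortality has no Kaplan-Meier or other time-to-event analysis at all.

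**Working it through.** The documents state no long-term mortality or dropout figure, so there is nothing of the plan's own to reproduce. The sizes below rest on assumed inputs.

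**Inputs**
- N = 90 (SAP 3.4: "90 transplanted recipients in the study are expected to provide adequate power").
- Early deaths: 1 − 0.939 = 6.1%, from the INSPIRE control rate in SAP 12.1, placed in month 1 (assumption).
- Mortality at 36 months: 30%, range 20-40% (assumption). Constant hazard after month 1 (assumption).
- Dropout: a fraction d = 10%, range 5-20%, is assigned a dropout time uniform over months 0-36 and independent of death risk (assumption).
- The baseline covariates carry no information about death (assumption).

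**Survival curve.** For t ≥ 1, S(t) = 0.939 × exp(−h(t − 1)), with h = −ln(0.70/0.939)/35 = 0.00839 per month. F(t) = 1 − S(t).

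**One recipient last seen alive at month 24.** S(24) = 0.774, so the remaining risk to month 36 is 1 − 0.700/0.774 = 9.6%. The baseline-only model imputes about 30%. With 20% and 40% mortality the remaining risk is 5.3% and 14.2%, against about 20% and 40% imputed.

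**Whole cohort.** Let D be the proportion with an observed death by t, A the proportion observed alive at t, and K = 1 − D − A the proportion lost. The model draws the lost at the death rate of those with known status, so the completed percentage has expectation D + K × D/(D + A) = D/(D + A). Here
- A(t) = S(t) × (1 − d × t/36)
- D(t) = (1 − d) × F(t) + d × (average of F(min(C, t)) over dropout time C)

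At month 36 the average of F over 0-36 months is 0.182. So D = 0.9 × 0.30 + 0.1 × 0.182 = 0.2882, A = 0.9 × 0.70 = 0.630, and D/(D + A) = 0.2882/0.9182 = 31.4%, against a true 30.0%.

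| Month | True | D | A | Completed | Excess (points) |
|---|---|---|---|---|---|
| 6 | 10.0% | 9.9% | 88.5% | 10.1% | +0.1 |
| 12 | 14.4% | 14.2% | 82.8% | 14.7% | +0.3 |
| 24 | 22.6% | 22.0% | 72.3% | 23.4% | +0.8 |
| 36 | 30.0% | 28.8% | 63.0% | 31.4% | +1.4 |

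**Range at month 36 (excess, points)**

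| True mortality | 5% dropout | 10% | 20% |
|---|---|---|---|
| 20% | +0.5 | +1.1 | +2.5 |
| 30% | +0.7 | +1.4 | +3.1 |
| 40% | +0.7 | +1.5 | +3.4 |

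**Simulation check** (4,000 trials of 90 recipients, 20 imputations, 30% mortality, 10% dropout; about 7.4 recipients lost per trial): imputation 31.5%, Kaplan-Meier 30.1%, deaths divided by all 90 recipients 28.9%. Kaplan-Meier recovers the truth, and a plain count over the full population understates it.

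**When the bias disappears.** In the worked case K = 1 − 0.2882 − 0.630 = 0.0818. Under non-informative dropout the lost recipients truly contribute 0.300 − 0.2882 = 0.0118 further deaths, a proportion of 0.0118/0.0818 = 14.4%. The model assigns 31.4%. If, other quantities held fixed, the lost recipients really die at 31.4% by month 36, about 2.2 times the non-informative figure, the excess is zero. Above that, mortality is understated.

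**Scale.** The exact 95% interval for 27/90 is 20.8% to 40.6%, about 20 points wide.

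No size was computed for lung graft-related mortality. The mechanism is the same, with the added complication that death from another cause competes with it.

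**The case against.** The strongest reply is that little depends on this. The endpoints are descriptive, with no hypothesis or performance goal, and largely post-market. SAP 5.3 does not expect missing outcomes. Protocol 7.3 allows phone contact and calls for review of the medical record, which helps to recover vital status. The same section of the SAP already plans a Kaplan-Meier display, so a sound estimate will be in the report. An excess of 1.4 points is small beside an interval 20 points wide. All of this stands, and it limits the weight of the point. It does not settle which figure is the reported mortality, and it does not cover lung graft-related mortality.

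A reader might infer more than the documents support:

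- *That mortality is overstated whenever anyone is lost.* The direction depends on dropout being unrelated to death risk and on imputation being applied to these endpoints. If sicker recipients are lost, the bias shrinks or reverses; if deaths are simply divided by all recipients, mortality is understated.
- *That all four time points are affected alike.* On the worked assumptions the excess at months 6 and 12 is 0.3 points or less.
- *That a recipient lost at month 30, with about 5% risk remaining, is typical.* No contact is scheduled then; last seen alive at month 24 is the natural case.
- *That completed data will show recipients dead at 24 months and alive at 36.* This needs each time point to be imputed separately. The SAP names no algorithm and neither requires nor excludes this.

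**Conclusion.** The point holds in a conditional form. Following SAP 12.4 and 5.3 as written overstates later mortality if dropout is unrelated to death risk: about +1.4 points at month 36 for 30% mortality and 10% uniform dropout, and +0.5 to +3.4 points across the ranges examined. Mortality level, dropout rate, shape of the curve and uninformative covariates are all assumptions. With no dropout the bias is zero.

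No trial conclusion turns on these endpoints. The change is still worth making, because the estimator that recovers the truth under the same assumptions is already planned as a display. It lacks only a named time-point estimate and interval, and a statement that it is the reported figure. The gap is clearest for lung graft-related mortality, which has no analysis that allows for censoring.

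**What to change.** Amend the SAP wording:

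1. **SAP 12.4, all-cause mortality.** Report the 6, 12, 24 and 36 month values as one minus the Kaplan-Meier estimate with a log-log (Greenwood) 95% confidence interval, censoring at the date last known alive.
2. **SAP 12.4, lung graft-related mortality.** Report it as a cumulative incidence (Aalen-Johansen) at the same time points, with death from other causes as a competing event.
3. **SAP 5.3.** Limit multiple imputation to outcomes through Day 30 or initial hospital discharge.

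Cost: SAP text and a small amount of extra programming. The planned Kaplan-Meier analyses already imply that event and last-contact dates will be available, though the documents do not list a date last known alive, so the case report form should be checked for it. The intervals for these endpoints would no longer be exact binomial.
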